8.1 Screening

Re-screening is permitted if the patient is not eligible for SARS-CoV-2 vaccination (initial vaccination or booster vaccine) by local regulation within 12 weeks after screening. In this case the Novartis Medical Advisor should be contacted to discuss further proceeding.

8.1.1 Eligibility screening

At screening, patients will be asked about previous COVID-19 disease. If a patient has had COVID-19 disease before screening, the patient is not eligible to further participate in the study.

8.1.2 Information to be collected on screening failures

Participants who sign an informed consent form and subsequently found to be ineligible will be considered a screen failure. The reason for screen failure should be entered on the applicable Case Report Form. The demographic information, informed consent, and Inclusion/Exclusion pages must also be completed for screen failure participants. No other data will be entered into the clinical database for participants who are screen failures, unless the participant experienced a serious adverse event during the screening phase (see SAE section for reporting details).

8.2 Participant demographics/other baseline characteristics

Anamnesis, participant demographics (year of birth, sex, race) and relevant medical history/current medical conditions including MS disease and current treatment will be documented.

All prescription medications, over-the-counter drugs and significant non-drug therapies prior to the start and during the study must be documented. See the protocol Section 6.2.1 Concomitant Therapy for further details on what information must be recorded on the appropriate page of the eCRF.

8.3 Efficacy

Blood samples will be collected at the timepoints defined in the Assessment Schedule (cohort 1a: Table 8-1, cohort 1b: Table 8-2, cohort 2a: Table 8-3, cohort 2b: Table 8-4). Follow instructions outlined in the Laboratory manual regarding sample collection, numbering, processing, and shipment.

8.3.1 Efficacy assessment 1

SARS-CoV-2 vaccination efficacy is defined as detection of SARS-CoV-2 specific T-cells one month after completion of the initial vaccination cycle or 1 month after a booster vaccination.

8.3.2 Efficacy assessment 2

Additional efficacy assessments are:

- Longitudinal follow-up of SARS-CoV-2 specific T-cells one week, one month, six months, 12 months and 18 months after second dose of vaccine as well as 6 months and 12 months after booster vaccine
- Longitudinal follow-up of SARS-CoV-2 serum functional antibody levels one week, one month, six months, 12 months and 18 months after second dose of vaccine as well as 6 months and 12 months after booster vaccine
- Phenotypical characterization of peripheral blood mononuclear cells for CD45, CD3, CD4, CD8, CD62L, CD45RA, CD27, CCR7
- Immunophenotyping for naive, central memory, effector memory, and effector cells on CD4⁺ and CD8⁺ cells
- Measuring cells positive for intracellular cytokine-staining for interferon-gamma and interleukin-4

8.3.3 Appropriateness of efficacy assessments

Efficacy assessments in KYRIOS are based on the study set up of the phase II clinical trial NCT04380701 (EudraCT: 2020-001038-36) for the SARS-CoV-2 vaccination candidate BNT162b2 (Sahin, Muik et al. 2020). This study reports SARS-CoV-2 specific T-cell responses one week after completion of the vaccination cycle measured by ex vivo IFN γ ELISPOT assay. Sahin et al. further characterized the T cells involved in the T cell response with regards to surface markers and Th1/Th2 polarization and reported stable IgG levels from one week after the second vaccine for up to 60 days. Comparable results were also reported for mRNA-1273 by Jackson et al, 2020.

The detection of SARS-CoV-2 reactive T-cells one month after completion of the vaccination cycle was chosen as a primary endpoint in this study to assess efficacy.

Further characterization of the T-cell response as well as measurement of IgG antibodies as reported by Sahin et al. will be performed as secondary assessments.

8.4 Safety

Safety assessments are specified below with the assessment schedule detailing when each assessment is to be performed.

For details on AE collection and reporting, refer to AE section.

Assessment	Specification
Physical examination	
A complete physical examination will include the examination of vital signs (blood pressure [SBP and DBP] and pulse), general appearance, height, weight, skin, neck (including thyroid), eyes, ears, nose, throat, lungs, heart, abdomen, back, lymph nodes, extremities, vascular, and neurological. If indicated based on medical history and/or symptoms, rectal, external genitalia, breast, and pelvic exams will be performed.
 
A short physical exam will include the examination of general appearance and vital signs (blood pressure [SBP and DBP] and pulse).
 
Information for all physical examinations must be included in the source documentation at the study site. Clinically relevant findings that are present prior to signing informed consent must be recorded on the appropriate CRF that captures medical history. Significant findings made after signing informed consent which meet the definition of an Adverse Event must be recorded as an adverse event.

8.4.1 Laboratory evaluations

A central laboratory will be used for analysis of all safety specimens collected. Details on the collection, shipment of samples and reporting of results by the central laboratory are provided to investigators in the central laboratory manual.

All abnormal lab results must be evaluated for criteria defining an adverse event and reported as such if the criteria are met. For those lab adverse events, repeated evaluations are mandatory until normalization of the result(s) or until the result is no longer considered clinically significant.

Special clinical laboratory evaluations

Test Category	Test Name
SARS-CoV-2 vaccination antibody response	Serum functional SARS-CoV-2 antibodies
SARS-CoV-2 vaccination T-cell response	Ex vivo IFNy and IL-2 enzyme-linked immunosorbent spot (ELISpot)
Hematology	Blood samples will be collected according to the schedule in Table 8-1, 8-2, 8-3 and Table 8-4. Hematocrit, Hemoglobin, Platelets, Red blood cells, White blood cells, Differential (Basophils, Eosinophils, Lymphocytes, Monocytes, Neutrophils)
B cell count	CD19+/CD20+ B-cell counts. Samples will be collected according to the schedule in Table 8-1, Table 8-2, Table 8-3 and Table 8-4.

8.4.2 Pregnancy and assessments of fertility

All pre-menopausal women who are not surgically sterile will have pregnancy testing. Additional pregnancy testing might be performed if requested by local requirements.

8.5 Additional assessments

No additional tests will be performed on participants entered into this study.

9 Study discontinuation and completion

9.1 Discontinuation and completion

9.1.1 Study treatment discontinuation and study discontinuation

Discontinuation of study treatment for a participant occurs when study treatment is stopped earlier than the protocol planned duration and can be initiated by either the participant or the investigator.

The investigator must discontinue study treatment for a given participant if, he/she believes that continuation would negatively impact the participant's well-being.

Study treatment must be discontinued under the following circumstances:

- Participant/guardian decision
- Pregnancy
- Use of prohibited treatment as per recommendations in the prohibited treatment section
- Any situation in which study participation might result in a safety risk to the participant

If discontinuation of study treatment occurs, the investigator should make a reasonable effort to understand the primary reason for the participant's premature discontinuation of study treatment and record this information.

Participants who discontinue study treatment or who decide they do not wish to participate in the study further should NOT be considered withdrawn from the study UNLESS they withdraw their consent (see Section 9.1.2 'Withdrawal of Informed Consent' section). **Where possible, they should return for the assessments indicated** in the Assessment Schedule. If they fail to return for these assessments for unknown reasons, every effort (e.g. telephone, e-mail, letter) should be made to contact the participant/pre-designated contact as specified in the lost to follow-up section. This contact should preferably be done according to the study visit schedule.

If the participant cannot or is unwilling to attend any visit(s), the site staff should maintain regular telephone contact with the participant, or with a person pre-designated by the participant. This telephone contact should preferably be done according to the study visit schedule.

After study treatment discontinuation, at a minimum, in abbreviated visits, the following data should be collected at clinic visits or via telephone/email contact:

- New / concomitant treatments
- Adverse Events / Serious Adverse Events (including COVID-19 disease)

9.1.1.1 Replacement policy

Patients successfully screened who do not receive a SARS-CoV-2 mRNA vaccination or a booster vaccine within 3 months after screening will be excluded from the study and be replaced unless the patient is currently not eligible for SARS-CoV-2 vaccination by local regulation. In this case the Novartis Medical Advisor should be contacted to discuss further proceeding.

9.1.2 Withdrawal of informed consent

Participants may voluntarily withdraw consent to participate in the study for any reason at any time. Withdrawal of consent occurs only when a participant:

- Does not want to participate in the study anymore,
and
- Does not want any further visits or assessments
and
- Does not want any further study related contacts

In this situation, the investigator should make a reasonable effort (e.g. telephone, e-mail, letter) to understand the primary reason for the participant's decision to withdraw his/her consent and record this information.

Where consent to the use of personal and coded data is not required, participant therefore cannot withdraw consent. They still retain the right to object to the further use of personal data.

Study treatment must be discontinued and no further assessments conducted, and the data that would have been collected at subsequent visits will be considered missing.

Further attempts to contact the participant are not allowed unless safety findings require communicating or follow-up.

All efforts should be made to complete the assessments prior to study discontinuation. A final evaluation at the time of the participant's study discontinuation should be made as detailed in the assessment table.

The patient can decide if Novartis is allowed to retain and use all research results (data) that have already been collected for the study evaluation or if stored blood samples need to be destroyed.

9.1.3 Lost to follow-up

For participants whose status is unclear because they fail to appear for study visits without stating an intention to discontinue or withdraw, the investigator must show "due diligence" by documenting in the source documents steps taken to contact the participant, e.g. dates of telephone calls, registered letters, etc. A participant should not be considered as lost to follow-up until due diligence has been completed or until the end of the study.

9.1.4 Early study termination by the sponsor

The study can be terminated by Novartis at any time.

Reasons for early termination:

- Unexpected, significant, or unacceptable safety risk to participants enrolled in the study
- Decision based on recommendations from applicable board(s) after review of safety and efficacy data

In taking the decision to terminate, Novartis will always consider participant welfare and safety. Should early termination be necessary, participants must be seen as soon as possible and treated as a prematurely withdrawn participant. The investigator may be informed of additional procedures to be followed in order to ensure that adequate consideration is given to the protection of the participant's interests. The investigator or sponsor depending on local regulation will be responsible for informing IRBs/IECs of the early termination of the trial.

9.2 Study completion and post-study treatment

Study completion is defined as when the last participant finishes their Study Completion visit and any repeat assessments associated with this visit have been documented and followed-up appropriately by the Investigator or, in the event of an early study termination decision, the date of that decision.

10 Safety monitoring and reporting

10.1 Definition of adverse events and reporting requirements

10.1.1 Adverse events

An adverse event (AE) is any untoward medical occurrence (e.g. any unfavorable and unintended sign [including abnormal laboratory findings], symptom or disease) in a clinical investigation participant after providing written informed consent for participation in the study. Therefore, an AE may or may not be temporally or causally associated with the use of a medicinal (investigational) product.

The investigator has the responsibility for managing the safety of individual participant and identifying adverse events.

Novartis qualified medical personnel will be readily available to advise on trial related medical questions or problems.

The occurrence of adverse events must be sought by non-directive questioning of the participant at each visit during the study. Adverse events also may be detected when they are volunteered by the participant during or between visits or through physical examination findings, laboratory test findings, or other assessments.

Adverse events must be recorded under the signs, symptoms, or diagnosis associated with them, accompanied by the following information (as far as possible) (if the event is serious refer to Section 10.1.2):

1. The Common Toxicity Criteria (CTC) AE grade (version 5 or higher):

Adverse events will be assessed and graded according to the Common Terminology Criteria for Adverse Events (CTCAE) version. CTCAE grade 5 will be used to capture death information within the eCRF.

2. Its relationship to the study treatment. If the event is due to lack of efficacy or progression of underlying illness (i.e. progression of the study indication) the assessment of causality will usually be 'Not suspected.' The rationale for this guidance is that the symptoms of a lack of efficacy or progression of underlying illness are not caused by the trial drug, they happen in spite of its administration and/or both lack of efficacy and progression of underlying disease can only be evaluated meaningfully by an analysis of cohorts, not on a single participant
3. Its duration (start and end dates) or if the event is ongoing, an outcome of not recovered/not resolved must be reported
4. Whether it constitutes a SAE (see Section 10.1.2 for definition of SAE) and which seriousness criteria have been met
5. Action taken regarding with study treatment.

All adverse events must be treated appropriately. Treatment may include one or more of the following:

- Dose not changed
- Dose Reduced/increased
- Drug interrupted/withdrawn

6. Its outcome (i.e. recovery status or whether it was fatal)

Conditions that were already present at the time of informed consent should be recorded in medical history of the participant.

Adverse events (including lab abnormalities that constitute AEs) should be described using a diagnosis whenever possible, rather than individual underlying signs and symptoms.

Adverse event monitoring should be continued for at least 30 days following the last dose of study treatment.

Once an adverse event is detected, it must be followed until its resolution or until it is judged to be permanent (e.g. continuing at the end of the study), and assessment must be made at each visit (or more frequently, if necessary) of any changes in severity, the suspected relationship to the interventions required to treat it, and the outcome.

Information about adverse drug reactions for the investigational drug can be found in the Investigator's Brochure (IB).

Abnormal laboratory values or test results constitute adverse events only if they fulfill at least one of the following criteria:

- they induce clinical signs or symptoms
- they are considered clinically significant
- they require therapy

Clinically significant abnormal laboratory values or test results must be identified through a review of values outside of normal ranges/clinically notable ranges, significant changes from baseline or the previous visit, or values which are considered to be non-typical in participant with the underlying disease.

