Study treatment	
 • Cohort 1: RNA vaccine will be received as part of clinical routine before starting Ofatumumab (OMB157) treatment 
 ○ Cohort 1a: will receive their 1st and 2nd SARS-CoV-2 vaccines (and an optional booster vaccine) ○ Cohort 1b: will receive a booster vaccine • Cohort 2: RNA vaccine will be received as part of clinical routine while already stable on Ofatumumab (OMB157) treatment 
 ○ Cohort 2a: will receive their 1st and 2nd SARS-CoV-2 vaccines (and an optional booster vaccine) ○ Cohort 2b: will receive a booster vaccine

Treatment of interest	Ofatumumab (OMB157) / SARS-CoV-2 modRNA vaccine
Efficacy assessments	
• Detection of SARS-CoV-2 specific T-cells• Detection of SARS-CoV-2 serum functional antibodies
Key safety assessments	Patients developing COVID-19
Data analysis	The primary analysis will not use any statistical testing or modelling. The absolute numbers and the proportion of participants achieving seroconversion within each cohort will be calculated. It will be augmented by a (descriptive) 95% confidence interval (exact Clopper-Pearson). All secondary endpoints will be summarized descriptively as frequencies and percentages, or, for continuous data, mean, standard deviation, median, minimum, and maximum will be presented.
Key words	COVID-19, SARS-CoV-2, RNA vaccine, ofatumumab, relapsing remitting multiple sclerosis, SARS-CoV-2 booster

1 Introduction

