2.1.1 General definitions

Study treatments

The modRNA vaccine and the ofatumumab treatment are defined both as study treatments. The ofatumumab treatment which is started either before or after receiving a SARS-CoV-2 mRNA vaccine (either initial or booster) is considered as treatment of interest.

Screening failure

A screening failure is a patient not eligible for the study. Screening failures are identified by:

- any inclusion criterion is violated or
- any exclusion criterion applies

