2.9.1 Adverse events (AEs)

According to the CSP all adverse events starting in the on-treatment period, i. e. the treatment-emergent AEs, are analyzed.

The on-treatment period lasts from the date of first administration of study treatment⁴ after informed consent to 30 days after the last visit.

⁴ Study treatment is ofatumumab as well as the modRNA vaccine.

The number (and percentage) of subjects with treatment-emergent adverse events will be summarized in the following ways:

- by treatment group (cohort 1 and 2), primary system organ class and preferred term.
- by treatment group (cohort 1 and 2), primary system organ class, preferred term and maximum severity
- by type of modRNA (Biontech/Pfizer versus Moderna), primary system organ class and preferred term.

A subject with multiple AEs within a MedDRA primary system organ class is only counted once towards the total of the primary system organ class.

A subject with multiple AEs within a preferred term is only counted once towards the total of the preferred term class.

Separate summaries will be provided for study medication related AEs, death, SAEs, AEs leading to discontinuation and adverse events leading to dose adjustment.

The absolute and relative frequency of COVID-19 infections is presented.

Deaths and serious adverse events are listed in addition. Deaths outside the on-treatment period are listed in addition.

Rates of COVID-19 infections and the rate of COVID-19 infections starting ≥ 7 days after the 2nd vaccination are displayed. All COVID-19 infections are listed with the dates of all COVID-19 vaccinations.

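### One causality judgement covers two study treatments, so the related-AE summary cannot describe the tolerability of ofatumumab separately from that of the vaccine

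*Protocol*

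**What the plan says.** Protocol 10.1.1 lists what is recorded with each adverse event. Item 2 is "Its relationship to the study treatment. If the event is due to lack of efficacy or progression of underlying illness". The sentence continues "i.e. progression of the study indication) the assessment of causality will usually be" *Not suspected*. The reason given is that lack of efficacy and disease progression "can only be evaluated meaningfully by an analysis of cohorts, not on a single participant".

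On what study treatment means, SAP 2.1.1 states: "The modRNA vaccine and the ofatumumab treatment are defined both as study treatments". A footnote in SAP 2.9.1 repeats it for the AE analysis: "Study treatment is ofatumumab as well as the modRNA vaccine". Protocol Table 6-1 lists both products as investigational. SAP 2.1.1 adds that ofatumumab "is considered as treatment of interest".

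On reporting, SAP 2.9.1 says: "Separate summaries will be provided for study medication related AEs, death, SAEs, AEs leading to discontinuation", and Protocol 12.5.1 plans the same. Neither splits relatedness by product. The key safety assessment in the Protocol summary is "Patients developing COVID-19".

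**The concern.** A single causality item suits a trial with one investigational product. Here there are two, and their expected adverse reactions have nothing to do with each other. If the form follows the protocol wording, a yes says only that at least one of the two was suspected. Describing safety and tolerability is a stated secondary objective, and the related-AE summary is the only planned AE table that uses the investigator's attribution. A reader would take it as information on ofatumumab, but could not tell how much of it reflects vaccine reactions.

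The lack-of-efficacy guidance adds a second difficulty. COVID-19 after vaccination can be seen as the vaccine failing to protect. It can also be seen as a possible consequence of B-cell depletion, and a reduced vaccine response under such therapy is the major concern set out in Protocol 1.1. One answer cannot record both views.

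**Working it through.** No figure in the plan bears on this point, so the check sets the texts side by side.

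1. **Judgement requested.** Protocol 10.1.1 item 2 asks for one relationship, in the singular. Its rationale also speaks of one trial drug. No section of either document asks for relatedness to each product.

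2. **Meaning of study treatment.** Protocol Table 6-1, SAP 2.1.1 and the SAP 2.9.1 footnote all include both products. SAP 5.2 starts the on-treatment period at the vaccination or the ofatumumab dose, whichever is earlier.

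3. **What the summary can show.** Write V = 1 if the vaccine is suspected and O = 1 if ofatumumab is suspected. Assuming an event is marked related when either is suspected, the recorded value is R = 1 if V = 1 or O = 1:
   - V = 1, O = 0 gives R = 1
   - V = 0, O = 1 gives R = 1
   - V = 1, O = 1 gives R = 1
   - V = 0, O = 0 gives R = 0

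   Three different situations give the same entry. The number of patients with R = 1 is therefore only an upper limit for the number with an ofatumumab-related event. The lower limit is zero.

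4. **Whether existing splits help.** SAP 2.1 presents all tables by cohort, but patients in both cohorts are planned to receive both products, so a cohort split is not a product split. SAP 2.9.1 also tabulates treatment-emergent events by vaccine brand, which does not separate ofatumumab.

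5. **Where dates help.** In Protocol section 3, cohort 1 is planned to start ofatumumab four weeks after the second vaccination (1a) or the booster (1b), and two weeks at the earliest. Events before that first dose cannot be due to ofatumumab. From the study vaccination onward, cohort 2 is exposed to both, and so is cohort 1 if further boosters follow. Dates cannot settle attribution there.

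6. **The lack-of-efficacy guidance.** It has two limbs: lack of efficacy, and progression of the underlying illness. The bracket about the study indication follows the second limb. The first limb names no product, while Protocol 8.3.1 defines efficacy in terms of vaccination. An investigator could therefore treat COVID-19 after vaccination as lack of efficacy and code it *Not suspected*. An investigator who reads the whole rule as concerning MS would not. The text decides neither way.

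7. **Which outputs depend on the answer.**
   - Dependent: the related-AE summaries; the sponsor's possible urgent queries on previously undocumented SAEs thought to be related; and reporting of SAEs after the 30-day period (Protocol 10.1.3).
   - Not dependent: all treatment-emergent AE tables by cohort, by maximum severity and by vaccine brand; COVID-19 counts and percentages; the rate of COVID-19 starting at least 7 days after the second vaccination; and the listing of every COVID-19 case with its vaccination dates (SAP 2.9.1).

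**The case against.** The best defence is that little depends on this summary. COVID-19 is reported in full without regard to causality, which is the cohort-level assessment that the rationale in item 2 calls for. All treatment-emergent events are tabulated by cohort whatever the attribution, and cohort 1 has a vaccine-only period. The objective is descriptive. Separate opinions per product in an open-label, non-randomised study would still not establish what ofatumumab caused. The case report form and the table shells are not among the documents, so separate fields may exist. A new field would also come late: Amendment 3 stopped recruitment, and SAP 5.1 cites 2023 notes to file that correct collected data.

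Most of this stands, and it limits the point without removing it. Nothing in either document requires a judgement per product, and the planned summary has no product split even if the data would allow one. The argument about timing bears on the protocol change more than on the SAP table, which can still be changed.

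A reader might go further and infer three things that the documents do not support:

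- **That COVID-19 is coded *Not suspected* by rule.** The guidance says usually, does not name COVID-19 and does not say whose efficacy it means. It leaves an ambiguity and sets no default.
- **That MS events soon after a vaccine dose are lost as disease progression.** Relapses have their own form, unusually severe or unexpected ones that warrant notification need an SAE form (Protocol 10.1.3), and SAP 2.7.1 reports the crude annual relapse rate.
- **That this one item decides SAE reporting.** Every SAE from consent to 30 days after the last visit is reported regardless of causality, apart from the relapse exemption in Protocol 10.1.3.

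**Conclusion.** The point holds within limits. Followed as written, the plan yields a related-AE summary that pools vaccine-related and ofatumumab-related events. It therefore cannot describe the tolerability of ofatumumab, and the problem is greatest in cohort 2. The lack-of-efficacy guidance is ambiguous about which product it concerns, which leaves the coding of COVID-19 after vaccination to the individual investigator.

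The size is modest. One family of descriptive safety summaries and some causality-dependent follow-up are affected. The primary endpoint, the COVID-19 outputs and the all-causality AE tables are not. No percentage can be attached, because the documents give no expected rate of reactions to either product. The conclusion assumes that the form follows the protocol's singular wording. If causality was collected per product, only the SAP summary and the guidance need correction.

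**What to change.** - **SAP 2.9.1, causality recorded per product:** replace the single related-AE summary with one for ofatumumab-related and one for vaccine-related events.
- **SAP 2.9.1, one field only:** split related AEs by exposure, using dates already held: onset before the first ofatumumab dose in cohort 1; onset within a pre-stated number of days after a vaccine dose; all other. Show COVID-19 on its own line whatever causality was recorded. Label this as a split by exposure, since it does not establish attribution where both products are on board.
- **Protocol 10.1.1 item 2:** ask for relatedness to each product separately, and state that the lack-of-efficacy guidance applies only to the product whose efficacy is lacking.

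The cost is either two judgements per event, made retrospectively where data are already collected, or one extra derivation. Either way there is one more table and some wording changes. No visits or patients are added. Retrospective judgements in an open-label study may be coloured by knowledge of outcomes, so the date-based split is the safer choice if only one field exists.
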